6. STUDY VACCINE AND ADMINISTRATION

6.1. Description of study vaccine

The candidate vaccine to be used has been developed and manufactured by GSK Biologicals.

The Quality Control Standards and Requirements for the candidate vaccine are described in separate Quality Assurance documents (e.g. release protocols, certificate of analysis) and the required approvals have been obtained.

The vaccines are labelled and packed according to applicable regulatory requirements.

[Table 10](#) presents the details of the study vaccine and administration.

Table 10 Study vaccine

Treatment name	Vaccine name	Formulation	Presentation	Volume to be administered	Number of doses
Boostrix	dTpa	DT>=2IU; TT>=20IU; PT=8µg; FHA=8µg; PRN=2.5µg; Aluminium=500µg Al3+	Pre-filled syringes, Homogeneous turbid white suspension	0.5 ml	1

DT: Diphtheria toxoid, TT: Tetanus toxoid, PT: Pertussis toxoid, FHA: Filamentous haemagglutinin, PRN: Pertactin, Aluminium as Al(OH)₃.

6.2. Storage and handling of study vaccine

The study vaccine must be stored at the respective label storage temperature conditions in a safe and locked place. Access to the storage space should be limited to authorised study personnel. The storage conditions will be assessed during pre-study activities under the responsibility of the sponsor study contact. The storage temperature should be continuously monitored with calibrated (if not validated) temperature monitoring device(s) and recorded. Refer to the Module on Clinical Trial Supplies in the SPM for more details on storage of the study vaccine.

Temperature excursions must be reported in degree Celsius.

Any temperature excursion outside the range of 0.0 to +8.0°C (for +2 to +8°C/+36 to +46°F label storage condition) or above -15.0°C (for -20°C/-4°F label storage condition) impacting investigational medicinal products (IMPs) must be reported in the appropriate (electronic) temperature excursion decision form (ATEAM). The impacted IMPs must not be used and must be stored in quarantine at label temperature conditions until usage approval has been obtained from the sponsor.

In case of temperature excursion below +2.0°C down to 0.0°C impacting IMP(s) there is no need to report in ATEAM, but adequate actions must be taken to restore the +2 to +8°C/+36 to +46°F label storage temperature conditions. The impacted IMP(s) may still be administered, but the site should avoid re-occurrence of such temperature excursion. Refer to the Module on Clinical Trial Supplies in the SPM for more details on actions to take.

Refer to the Module on Clinical Trial Supplies in the SPM for details and instructions on the temperature excursion reporting and usage decision process, packaging and accountability of the study vaccine.

6.3. Dosage and administration of study vaccine

The vaccine will be administered as detailed in [Table 11](#).

The vaccine will be administered as an IM injection into the deltoid muscle of the non-dominant arm, i.e. in the left arm if the subject is right-handed or in the right arm if the subject is left-handed. In case it is not possible for a valid reason to inject in the non-dominant arm, an injection in the dominant arm may be performed. *Boostrix* should in no circumstances be administered intravascularly.

In order to ensure proper IM injection of the vaccine, a needle of 1-1½ inch length, 25 gauge will be used [[Zuckerman, 2000](#)]. Needle of 21-25 gauge can be used depending on the age of the subjects.

Table 11 Dosage and administration

Type of contact and timepoint	Volume to be administered	Study Group	Treatment name	Route	Site	Side
Visit 1 (Day 1)	0.5 ml	dTpa Group	Boostrix	IM	Deltoid	Non-dominant

IM: Intramuscular

6.4. Replacement of unusable vaccine doses

In addition to the vaccine doses provided for the planned number of subjects (including over-randomisation when applicable), at least 5% additional vaccine doses will be supplied to replace those that are unusable.

6.5. Contraindications to vaccination

Since this is a single dose study, contraindications to vaccination are included in the exclusion criteria. Refer to Section 4.3.

The following events constitute contraindications to administration of Boostrix at that point in time; if any of these events occur at the time scheduled for vaccination, the subject may be vaccinated at a later date, within the time window specified in the protocol (see Section 6.7.1), or the subject may be withdrawn at the discretion of the investigator (see Section 6.7.2).

- Acute disease and/or fever at the time of vaccination.
 - Fever is defined as temperature $\geq 38.0^{\circ}\text{C}$. The preferred location for measuring temperature in this study will be the axilla.
 - Subjects with a minor illness (such as mild diarrhoea, mild upper respiratory infection) without fever can be administered the study vaccine.

6.6. Warnings and precautions

As with all injectable vaccines, appropriate medical treatment should always be readily available in case of anaphylactic reactions following the administration of the vaccine. For this reason, the vaccinee should remain under medical supervision for 30 minutes after vaccination.

Boostrix vaccination should be administered with caution to subjects with thrombocytopenia or a bleeding disorder since bleeding may occur following an intramuscular (IM) administration to these subjects.

Boostrix vaccination should under no circumstances be administered intravenously.

6.7. Concomitant medications/products and concomitant vaccinations

At each study visit/contact, the investigator or delegate should question the subject and/or the subject's parent(s)/adoptive parent(s) about any medications/products taken and vaccinations received by the subject.

6.7.1. Recording of concomitant medications/products and concomitant vaccinations

The following concomitant medication(s)/product(s)/vaccine(s) must be recorded in the eCRF

- All concomitant medications/products, except vitamins and dietary supplements, administered during the period starting from the administration of study vaccine (Day 1) and ending at Visit 2 (Day 31).

- Any concomitant vaccination administered in the period starting from the administration of study vaccine (Day 1) and ending at the last study visit [Visit 2 (Day 31)].
- Prophylactic medication (i.e. medication administered in the absence of ANY symptom and in anticipation of a reaction to the vaccination).
 - E.g. an anti-pyretic is considered to be prophylactic when it is given in the absence of fever and any other symptom, to prevent fever from occurring [Fever is defined as temperature $\geq 38.0^{\circ}\text{C}$. The preferred location for measuring temperature in this study will be the axilla.
- Any concomitant medications/products/vaccines listed in Section 6.7.2.
- Any concomitant medications/products/vaccines relevant to a SAE to be reported as PP or administered at any time during the study period for the treatment of a SAE. In addition, concomitant medications relevant to SAEs need to be recorded on the expedited Adverse Event report in eCRF.

6.7.2. Concomitant medications/products/vaccines that may lead to the elimination of a subject from per protocol analyses

The use of the following concomitant medications/products/vaccines will not require withdrawal of the subject from the study but may determine a subject's evaluability in the PP analysis. See Section 10.4 for cohorts to be analysed.

- Any investigational or non-registered product (drug or vaccine) other than the study vaccine used during the study period.
- Immunosuppressants or other immune-modifying drugs administered chronically (i.e. more than 14 days) during the study period. For corticosteroids, this will mean prednisone ≥ 20 mg/day (for adult subjects) or ≥ 0.5 mg/kg/day (for paediatric subjects), or equivalent. Inhaled and topical steroids are allowed.
- Long-acting immune-modifying drugs administered at any time during the study period (e.g. infliximab).
- A vaccine not foreseen by the study protocol administered during the period starting from the dose of study vaccine (Day 1) and ending 31 days after the dose of vaccine administration, with the exception of influenza vaccine which is allowed throughout the study period.
- In case an emergency mass vaccination for an unforeseen public health threat (e.g.: a pandemic) is organised by the public health authorities, outside the routine immunisation program, the time period described above can be reduced if necessary for that vaccine provided it is licensed and used according to its Summary of Product Characteristics (SmPC) and according to the local governmental recommendations and provided a written approval of the Sponsor is obtained.
- Immunoglobulins and/or any blood products administered during the study period.

6.8. Intercurrent medical conditions that may lead to elimination of a subject from per protocol analyses

At each study visit subsequent to the vaccination visit, it must be verified if the subject has experienced or is experiencing any intercurrent medical condition. If it is the case, the condition(s) must be recorded in the eCRF.

Subjects may be eliminated from the PP cohort for immunogenicity if, during the study, they incur a condition that has the capability of altering their immune response or are confirmed to have an alteration of their initial immune status.

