The interval between study visits is presented in [Table 6](#).

Table 6 Intervals between study visits

Interval	Optimal length of interval ¹	Allowed interval ²
Visit 1→Visit 2	30 days	21 days-48 days

¹ Whenever possible the investigator should arrange study visits within this interval.

² An interval of 21-48 days between Visit 1 and Visit 2 will be considered for the Per Protocol (PP) cohort of immunogenicity. Refer to Section 10.4 for the definition of the cohorts for analysis. If subjects return for the visits prior to 30 days, they should take the diary card home and continue to record unsolicited safety information until 30 days post-vaccination and mail/send it upon completion. Investigators should transcribe any data already collected on the cards prior to sending it back home with the subjects. Investigators will make an attempt to retrieve diary cards from subjects who have not mailed/sent them in.

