5.6.12. Distribution of diary cards and recording of AEs, SAEs and pregnancies

- Refer to Section 8.3 for procedures for the investigator or delegate to record AEs, SAEs, and pregnancies. Refer to Section 8.4 for guidelines and how to report SAE, and pregnancy reports to GSK Biologicals.
- The subjects/subjects' parent(s)/adoptive parent (s) will be instructed to contact the investigator or delegate immediately should they/the subjects manifest any signs or symptoms they perceive as serious.
- At Visit 1, diary cards will be provided to the subject/subject's parent(s)/adoptive parent(s). The subject/subject's parent(s)/adoptive parent(s) will record body (preferably axillary) temperature and any solicited local/general AEs (i.e. on the day

of vaccination and during the next three days) or any unsolicited AEs (i.e. on the day of vaccination and during the next 30 days) occurring after vaccination. The subject/subject's parent(s)/adoptive parent(s) will be instructed to return the completed diary card to the investigator or delegate at the next study visit.

- Note: Diary cards can be filled in by a minor subject under the supervision of the subject's parent(s)/adoptive parent(s) provided that the minor has the competency to assess and report the information to be provided in the diary card. The ultimate accountability for the completion of the diary cards remains with the subject's parent(s)/adoptive parent(s). The investigator or delegate should discuss this accountability with the subject's parent(s)/adoptive parent(s).
- Collect and verify completed diary cards during discussion with the subject/subject's parent(s)/adoptive parent(s) on Visit 2.
 - Note: If the diary card has been filled in by a minor subject, the investigator or delegate should verify the reported information during a discussion with the minor subject preferably in the presence of his/her parent(s)/adoptive parent(s).

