8.5. Follow-up of adverse events, serious adverse events, and pregnancies

8.5.1. Follow-up of adverse events and serious adverse events

8.5.1.1. Follow-up during the study

After the initial AE/SAE report, the investigator is required to proactively follow each subject and provide additional relevant information on the subject's condition to GSK Biologicals (within 24 hours for SAEs; refer to [Table 17](#)).

All SAEs documented at a previous visit/contact and designated as not recovered/not resolved or recovering/resolving will be reviewed at subsequent visits/contacts until the end of the study.

All AEs documented at a previous visit/contact and designated as not recovered/not resolved or recovering/resolving will be reviewed at subsequent visits/contacts until 30 days after the vaccination.

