- For a given subject and the analysis of solicited symptoms during the 4-day post-vaccination follow-up period, missing or non-evaluable measurements will not be replaced. Therefore, the analysis of the solicited symptoms based on the TVC will include only vaccinated subjects and doses with documented safety data (i.e. symptom screen completed).
- For analysis of unsolicited AEs, such as SAEs or AEs by primary MedDRA term, and for the analysis of concomitant medications, all vaccinated subjects will be considered. Subjects who did not report the event or the concomitant medication will be considered as subjects without the event or the concomitant medication, respectively.
- For summaries reporting both solicited and unsolicited AEs, all vaccinated subjects will be considered. Subjects who did not report the event or the concomitant medication will be considered as subjects without the event or the concomitant medication, respectively.

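### Concomitant medication recording ends at Visit 2, which may fall on Day 22, yet the medication table covers Day 1-31 and counts unrecorded use as none

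*Protocol*

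**What the plan says.** Section 6.7.1 sets the recording period for concomitant medication (vitamins and dietary supplements excepted) as "administered during the period starting from the administration of study vaccine (Day 1) and ending at Visit 2 (Day 31"). The period for concomitant vaccination is tied to the visit in the same way: "ending at the last study visit [Visit 2 (Day 31").

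Table 6 in section 5.5 gives 30 days as the optimal interval and 21 to 48 days as the allowed one. Its footnote adds: "An interval of 21-48 days between Visit 1 and Visit 2 will be considered for the Per Protocol (PP) cohort of immunogenicity". For subjects who come back before 30 days, the same footnote says "they should take the diary card home and continue to record unsolicited safety information until 30 days post-vaccination and mail/send it upon completion", and then "Investigators will make an attempt to retrieve diary cards from subjects who have not mailed/sent them in".

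Section 10.8 plans a table, with exact 95% confidence intervals, of the percentage of subjects who started at least one medication over Day 1-4 and over Day 1-31. Section 10.5 keeps all vaccinated subjects in the denominator and states: "Subjects who did not report the event or the concomitant medication will be considered as subjects without the event or the concomitant medication, respectively".

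**The concern.** Section 6.7.1 writes Visit 2 and Day 31 as if they were the same day. They coincide only at the optimal interval. An early visit is a planned possibility: it lies inside the allowed interval and has its own instruction. For such a subject, a site that follows the text closes the medication record at the visit, while the analysis window stays open to Day 31.

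The days in between are not treated as missing. Under section 10.5 they count as days without medication, so the error has one direction: the reported 31-day percentage can fall short of the truth but cannot exceed it. A statistical analysis plan could not repair this, because the data would not have been collected.

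**Working it through.** **Inputs**

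- Visit 1 and vaccination: Day 1 (Table 5).
- Visit interval: 30 days optimal, 21 to 48 days allowed (Table 6).
- End of medication recording: Visit 2 (section 6.7.1).
- Analysis window: Day 1-31, 31 days (section 10.8).
- No report counts as no medication (section 10.5).
- Not given in the protocol, hence assumed below: the share of early returners, the true medication percentage and the timing of first use.

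**Step 1: reproduce the plan's own day.** Study day = 1 + interval. The optimal interval gives 1 + 30 = 31, so the Day 31 label is right for an on-time visit. The limits give 1 + 21 = 22 and 1 + 48 = 49.

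**Step 2: uncovered days.** For a visit on Day 22, the unrecorded days are 31 − 22 = 9 (Days 23 to 31), and 9/31 = 29.0% of the window.

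**Step 3: does anything else collect medication on those days?**

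- The early-return instruction in Table 6 covers unsolicited safety data only.
- Section 5.6.12 lists the diary contents as temperature, solicited events and unsolicited events. Medication is not among them.
- Section 6.7 has the investigator ask about medication at each visit or contact, but Table 5 schedules none after Visit 2.
- Section 6.7.1 separately requires recording of the products listed in section 6.7.2. The vaccine window there runs to 31 days after the dose, with influenza vaccine excepted, so most vaccines are covered.
- Medication relevant to a serious adverse event, or given to treat one, also has its own entry in section 6.7.1.

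What remains uncovered is mainly routine medication not linked to a serious adverse event.

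**Step 4: effect on the tabulated percentage.** Let p be the true proportion starting a medication within 31 days. With a constant rate of first start, the proportion recorded by Day 22 is p₂₂ = 1 − (1 − p)^(22/31). If a share e returns on Day 22 and the others on or after Day 31, the table shows e × p₂₂ + (1 − e) × p.

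For p = 30%: p₂₂ = 1 − 0.70^(22/31) = 22.4%. With e = 25%: 0.25 × 22.4% + 0.75 × 30% = 28.1%.

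| True 31-day percentage | Shown if a quarter return on Day 22 | Shown if all return on Day 22 |
|---|---|---|
| 10% | 9.3% | 7.2% |
| 30% | 28.1% | 22.4% |
| 50% | 47.2% | 38.9% |
| 70% | 66.9% | 57.4% |

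The relative loss is smaller than the 29% of days lost. At p = 70% with every subject on Day 22 it is (70 − 57.4)/70 = 18%, because a subject whose first medication was recorded before the visit is already counted. If first starts cluster soon after vaccination, the loss is smaller still. The Day 1-4 summary is unaffected, since no allowed Visit 2 falls before Day 22.

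**The case against.** The best defence is that section 6.7.1 also writes Day 31, so a site could read the period as running to that day whatever the visit date, and the continued diary might pick up medication in practice. That makes the text ambiguous, but it does not rescue it: the stated end point is the visit, and neither the early-return instruction nor the list of diary contents mentions medication.

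It can also be said that 30 days is the interval to aim for, so few subjects may return as early as Day 22, and that medication use is one descriptive table in a study whose analyses are all descriptive (section 10.9). Both points stand, and they limit the weight of the finding.

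A reader might go further and infer that the Day 1-31 adverse event summaries also lose up to 9 days. The protocol does not support that. Section 8.3.1 runs the recording of adverse events, serious adverse events and pregnancies to 30 days after the dose, independently of the visit. Table 6 continues the diary to the same point and requires attempts to retrieve cards. Section 8.5.1.1 requires proactive follow-up, and unresolved adverse events "will be reviewed at subsequent visits/contacts until 30 days after the vaccination". It is true that section 5.6.12 places the discussion of the card at Visit 2 ("Collect and verify completed diary cards during discussion with the" subject or parent), and that a card never returned would count as no event. That is a weaker check on late reports from early returners, not a recording window that closes early.

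**Conclusion.** The point holds for concomitant medication. Read as written, sections 6.7.1, 5.5, 10.8 and 10.5 together leave up to 9 of 31 days unrecorded for a subject who returns early, and score those days as free of medication. The 31-day percentage is then biased downwards.

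The 9 days follow from the protocol alone. The effect on the percentage does not: it rests on an assumed share of early returners and an assumed constant rate of first start. Under those assumptions a true 30% would show as 28.1% with a quarter of subjects at Day 22. The figure of 22.4%, with all subjects at Day 22, is the extreme for that true value and not an expectation.

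The adverse event, serious adverse event and pregnancy windows, the 4-day summaries and most concomitant vaccines are outside the finding. It is minor, because medication use is neither an objective nor a listed endpoint, but the contradiction is real and should be reconciled.

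**What to change.** In section 6.7.1, end the recording periods for concomitant medication and for concomitant vaccination at Visit 2 or 30 days after vaccination, whichever is later. In the Table 6 footnote, have the take-home diary of early returners also capture medication and vaccination until 30 days after vaccination, and list these items among the diary contents in section 5.6.12.

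The cost is a change of wording and slightly more diary data to transcribe for early returners. No visit or blood sample is added. A scheduled telephone call on or after Day 31 for early returners would be a reasonable extra, but it is a new procedure and is not needed to resolve this point.

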7. HEALTH ECONOMICS

Not applicable.

8. SAFETY

The investigator or site staff is/are responsible for the detection, documentation and reporting of events meeting the criteria and definition of an AE or SAE as provided in this protocol.

Each subject/subject's parent(s)/adoptive parent(s) will be instructed to contact the investigator immediately should they/the subject manifest any signs or symptoms they perceive as serious.

8.1. Safety definitions

8.1.1. Definition of an adverse event

An AE is any untoward medical occurrence in a clinical investigation subject, temporally associated with the use of a medicinal product, whether or not considered related to the medicinal product.

An AE can therefore be any unfavourable and unintended sign (including an abnormal laboratory finding), symptom, or disease (new or exacerbated) temporally associated with the use of a medicinal product. For marketed medicinal products, this also includes failure to produce expected benefits (i.e. lack of efficacy), abuse or misuse.

Examples of an AE include:

- Significant or unexpected worsening or exacerbation of the condition/indication under study.
- Exacerbation of a chronic or intermittent pre-existing condition including either an increase in frequency and/or intensity of the condition.
- New conditions detected or diagnosed after investigational vaccine administration even though they may have been present prior to the start of the study.

- Signs, symptoms, or the clinical sequelae of a suspected interaction.
- Signs, symptoms, or the clinical sequelae of a suspected overdose of either investigational vaccine or a concurrent medication (overdose per se should not be reported as an AE/SAE).
- Signs, symptoms temporally associated with vaccine administration.
- Significant failure of expected pharmacological or biological action.
- Pre- or post-treatment events that occur as a result of protocol-mandated procedures (i.e. invasive procedures, modification of subject's previous therapeutic regimen).

AEs to be recorded as endpoints (solicited AEs) are described in Section 8.1.3. All other AEs will be recorded as UNSOLICITED AEs.

Examples of an AE DO NOT include:

- Medical or surgical procedures (e.g. endoscopy, appendectomy); the condition that leads to the procedure is an AE/SAE.
- Situations where an untoward medical occurrence did not occur (e.g. social and/or convenience admission to a hospital, admission for routine examination).
- Anticipated day-to-day fluctuations of pre-existing disease(s) or condition(s) present or detected at the start of the study that do not worsen.
- Pre-existing conditions or signs and/or symptoms present in a subject prior to the study vaccination. These events will be recorded in the medical history section of the eCRF.

